#### 4.2.3.2. Determination of Maximum Tolerated Dose

The MTD will be defined as the highest dose level below the maximum administered dose where the number of patients with DLT is <2 out of 6. At least 6 patients evaluable for the safety endpoint must be entered at this dose level and a toxicity rate of less than 0.33 must be observed to be confirmed as the MTD.

#### 4.2.3.3. Recommended Phase 2 Dose (RP2D) Definition

An RP2D can be declared at any dose level or schedule where the MTD criteria were not met, yet clinical, PK, pharmacodynamics and/ or laboratory data indicate an optimal biologically active dose has been reached (with a toxicity rate of less than 0.33) and at least 6 patients have been treated at that given dose level.

## 4.2.4. Expansion Phase (Phase 2a) Study Design

Once all patients have completed Cycle 1 of the dose escalation phase (Phase 1), the SRC has reviewed all available safety, clinical, laboratory, and PK data and recommends continuing, and the MTD/RP2D of AFM24 in combination with atezolizumab has been determined, enrollment into the expansion cohorts for the selected cancer indications in the expansion phase (Phase 2a) will begin (Section 9.5.1).

A Simon two-stage optimal design will be utilized for EXP-1 and EXP-2. EXP-3 and EXP-4 are exploratory with no hypothesis testing. The expansion phase (Phase 2a) of the study is intended to collect preliminary evidence of efficacy and to further confirm the safety of AFM24 in combination with atezolizumab.

During the expansion phase (Phase 2a), up to 130 patients will receive weekly infusions of AFM24 at the RP2D in combination with every 2-weekly infusion of atezolizumab in 4-week cycles in the following 3 expansion phase cohorts based on tumor types:

- EXP-1 will enroll patients with advanced or metastatic *EGFR*-wild type (*EGFR*-WT) expressing NSCLC;
- EXP-2 will enroll patients with locally advanced, unresectable, or metastatic gastric or gastro-esophageal junction (GEJ) adenocarcinoma;
- EXP-3 will enroll patients with advanced or metastatic hepatocellular carcinoma (other than fibrolamellar and sarcomatoid subtype, Barcelona Clinic Liver Cancer Stage C disease or Stage B disease not amenable to locoregional therapy or refractory to locoregional therapy), hepatobiliary-, or pancreatic adenocarcinoma;
- EXP-4 will enroll patients with advanced or metastatic EGFR-mutated NSCLC

Patients will receive the investigational treatment (AFM24 + atezolizumab) until disease progression, intolerable toxicity, Investigator discretion, or patient withdrawal of consent.

Additional treatment schedules of AFM24 administration (e.g., q2w) may be explored as part of the expansion phase (Phase 2a) within or across cohorts.

An Independent Data Monitoring Committee (IDMC), consisting of clinical experts who are not directly involved in this clinical study, will be established for Phase 2a of the study. The IDMC will review all safety data generated throughout the dose expansion phase (Phase 2a) of the study

on a regular basis. Based on the outcome of their review, the IDMC will provide recommendations to the Sponsor regarding study conduct or study procedures. The set-up and operational process for this IDMC will be described in a separate IDMC charter.

The following stopping rules for the expansion phase (Phase 2a) part of the study apply:

- ≥ 3 patients report the same AE occurring within 30 days of starting study treatment meeting the DLT criteria in the same expansion cohort or
- ≥ 3 patients reported the same SAE with at least possible relationship to the study treatment occurring within 30 days of starting study treatment within the same expansion cohort, or
- any death with at least possible relationship to the study treatment occurring within 30 days of starting study treatment, or
- ≥ 30% patients experiencing the same SAE with at least possible relationship to the study treatment occurring within 30 days of starting study treatment across expansion cohorts.

If at least 1 of the stopping rules is met, patient recruitment will be paused. Patients who are already receiving study treatment and are deriving clinical benefit may continue study treatment at the discretion of the Investigator. The ICF will be updated with the new safety information, and the patients will be reconsented once the ICF is approved and available. Following the stop of patient enrollment, a thorough investigation will be done jointly by the Sponsor and the IDMC. The study will continue only if the IDMC confirms a positive benefit/risk assessment of the study treatment. Following a positive assessment by the IDMC, a substantial amendment will be submitted to the regulatory authority, and enrolment can be restarted only after approval by the regulatory authority.

In addition, all study treatments must be paused in any patient who experiences a TEAE meeting the DLT criteria regardless of when it occurs pending further evaluation by the Investigator and/or IDMC.

## 4.2.5. Follow-Up

Patients who are permanently discontinued from the study during the safety lead-in phase should complete the EOT visit and the safety follow-up visit but will not require the long-term follow-up.

#### 4.2.5.1. End of Treatment Visit

The EOT visit will be performed 14 days ( $\pm$  2 days) from the last drug intake or before the start of any new anti-cancer treatment; whichever is sooner. For patients who discontinue prematurely, before disease progression, it must be performed as the last visit. If the EOT visit coincides with a regular study visit, the EOT evaluations will supersede those of that scheduled visit, and the data should be entered in the EOT page in the electronic case report form (eCRF). The patient should be encouraged to return for the follow-up visit.

## 4.2.5.3. Long-Term Follow Up Period

Once a patient has confirmed disease progression the patient moves into the survival follow-up phase, the patient should be contacted by telephone, email or visit every 3-month intervals (±2 weeks) to assess for survival status until withdrawal of consent, death, or the end of the study, whichever occurs first.

#### 4.3. Number of Patients

The total number of patients planned for this study is estimated to be up to 148\*.

Each dose escalation cohort in Phase 1 will consist of 3 to 6 patients. Assuming 3 dose levels, there will be approximately 9 to 18 patients in the dose escalation part of the study (Phase 1). Following the determination of the RP2D, up to 130 additional patients will be treated in the dose-expansion part of the study (Phase 2a).

**Note:** \*Additional patients may be entered to replace DLT non-evaluable patients in Phase 1 and to replace patients not evaluable according to the Full Analysis Set (FAS). Thus, the actual number of patients entered may exceed 148, but will not exceed 179 patients entered.

# 4.4. Study Duration

The total study duration will be approximately 12 months to complete the dose escalation phase (Phase 1) and from 24 to 48 months to enroll patients in and subsequently complete the expansion Phase (Phase 2a).

Patients may receive the investigational study treatment (AFM24 + atezolizumab) until disease progression, intolerable toxicity, Investigator discretion, or patient withdrawal of consent.

Patients may continue treatment after disease progression at their assigned dose if there is continuing clinical benefit per Investigator's judgment and in consultation with the Sponsor's Medical Monitor.

# 4.5. Study Initiation and Completion

The start of this clinical study is defined as the first act of screening (signing of the Main ICF) for a potential subject.

The end of the study is defined as when all patients have completed the first long-term follow-up interval, withdrawn, or died, whichever occurs first.

In the expansion phase (Phase 2a) of this study, patients will participate in recurring 4-week cycles until disease progression, intolerable toxicity, death, or discontinuation from study, whichever occurs first.

Patients who die or complete the study follow-up through study closure will be considered to have "completed" the study.

The study will be analyzed and reported once all patients of the study have experienced at least one of the following:

- Has been treated until at least 4 weeks after the 1st post-baseline tumor assessment
- Disease progression
- Withdrawal from treatment due to a drug related AE
- Fatal event
- Lost to long-term follow-up
- Withdrawal of consent
- Start of other anti-cancer treatment

In case patients are still being treated with study medication at the final data cut-off date for this study, such patients will be kept on treatment in the study and data collected will then be reported in an addendum to the final clinical study report (CSR). It will be noted in the final CSR that such a revised report may be provided.

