# 4.2.2. Safety Lead-In Phase (for Both the Dose Escalation Phase [Phase 1] and the Expansion Phase [Phase 2a])

Seven days prior to Cycle 1 Day 1 (C1D1) (i.e., at Day -7), patients will receive a single dose of AFM24 (dose assigned to a given cohort) and will be observed for any AE for 1 week (from Day -7 through Day -1, the safety lead-in phase). Patients who have any Grade ≥3 cytokine release syndrome (CRS) or IRR symptoms lasting >6 hrs or any other possibly treatment-related Grade ≥3 non-hematological TEAEs or clinically significant hematological Grade ≥3 TEAEs during their

. Patient's eligibility criteria must be re-confirmed on or within 7 days before Day -7, before the administration of the first AFM24 infusion; please refer to inclusion and exclusion criteria sections (Sections 5.1 and 5.2, respectively) to see allowed time periods of screening assessments.

Patients not proceeding to combination therapy (AFM24 + atezolizumab) will be replaced.

Note: Patients are required to receive premedication approximately 1 hour before each dose of AFM24; a list of premedications is provided in Section 6.3.

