#### 8.3.2.5. Clinical Benefit Rate

Clinical benefit rate is measured per RECIST v1.1 criteria as the proportion of patients who achieve overall tumor response (CR or PR) or SD for at least 24 weeks.

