# 8.6. Disease Response Assessment

Disease response will be assessed by the Investigator, using RECIST v1.1. For both the dose escalation phase (Phase 1) and expansion phase (Phase 2a), imaging results will be collected and preserved for future independent central review, if needed. Tumor assessment with CT and/or MRI will occur at Screening as well as during the last week of Cycles 2, 4, 6, 8, 10, 12 and every 3 cycles thereafter. Partial or CR needs to be confirmed with repeated assessment at least 4 weeks after the initial assessment.

If initial radiological PD is observed, while the clinical condition of the patient is stable, treatment continuation is allowed at the discretion of the Investigator and in consultation with the Sponsor's Medical Monitor. If treatment is continued after initial PD, a confirmatory scan should be acquired

within 4-6 weeks. However, the first successive scheduled timepoint after the confirmatory scan may be skipped if the window is considered not clinically relevant (up to the discretion of the Investigator). The next subsequent timepoint following the skipped timepoint must adhere to the original schedule.

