## 9.3.2. Efficacy Analyses

Objective Response: The number and percentage of patients achieving each category of response for OR (including CR and PR) will be provided. Results will be presented by percentages and 95% CI.

Clinical benefit rate (defined as CR or PR [any duration] OR SD ≥24 weeks): Results will be presented by percentages and 95% CI.

Disease control rate (DCR) at months 3, 6, 9, 12 and 15, as defined by achieving CR and/or PR and/or SD assessed by RECIST v1.1 will be presented by percentage rates and where appropriate the 95% CIs.

Progression-free survival will be measured from the date of the first dose of AFM24 and atezolizumab study drug to the date of disease progression or death from any cause, whichever occurs first.

Overall survival will be measured from the date of the first dose of AFM24 study drug to the date of death for any cause.

Duration of response will be measured from the date at which response criteria are met for CR or PR until the date of recurrence, PD, or death. Progression-free survival, overall survival, and DOR will be summarized using the Kaplan-Meier method. Censoring rules will be provided in the statistical analysis plan.

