#### 8. ANALYTICAL PLAN AND STATISTICAL METHODS

#### 8.1 GENERAL CONVENTIONS AND STATISTICAL CONSIDERATIONS

All analyses will be performed using SAS® statistical analysis software (SAS, SAS/GRAPH and SAS/STAT; version 9.4 or higher of SAS for Windows [SAS Institute Inc.; Cary, NC, USA]).

Descriptive statistics for continuous variables will include the number of patients, mean, standard deviation, median, minimum, and maximum values. All raw data will be presented to the original number of decimal places. Means, medians, and confidence intervals will be presented to 1 more decimal place than in the raw data. Standard deviations will be presented to 2 more decimal places than in the raw data. Summary statistics for categorical variables will contain count and percentage. Percentages will be presented to one decimal, except for one hundred percent, which will be presented as 100%. Unless otherwise specified, percentages for baseline summaries will be based on the total number of patients in the treatment arm or

Review Status: Draft Version: 2.0 Version Date: 22-JUL-2024

overall, for the indicated population (dependent on table column heading), percentages for post-baseline summaries will be based on the total number of patients with non-missing values in the treatment arm or overall.

Change from Baseline at Visit X is defined as Test Value at Visit X – Baseline Value.

Unless otherwise stated, all analyses will be descriptive in nature, no formal statistical comparisons of data from different arms or cancer type will be done.

Data will be listed individually by patient.

The tables and the listings will be done separately for two phases. Phase 1 summaries will be presented by the dose level, and Phase 2a summaries by Expansion Cohort.

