The ORR (CR or PR), DCR (CR or PR or SD) and CBR (CR or PR or SD ≥24 weeks) assessed by the investigators using RECIST 1.1 will be summarized. The best overall response will be used to define the ORR, DCR and CBR. Best response is defined as the best observed response (CR>PR>SD>PD) throughout the study. See SAP table 1 for rules of response confirmation. Summaries will include the count and percentages and the 95% confidence intervals where appropriate of different best overall responses, ORR, DCR and CBR for each dose level. The percentages will be based on the total number of patients in the Full Analysis Set for a given Expansion Arm.

Waterfall and swimmer plots will also be created, similar to what is described for Phase 1, but additionally color coding of the Best Overall Response.

PK and ADA results matching Phase 1 secondary endpoints will be analyzed, but the presentation will be done by Expansion Cohort rather than by dose level. Analysis of Adverse Events is described in section 8.7.2.

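### If the final cut-off falls near the minimum in Protocol 4.5, patients who started in about the last 12 weeks of enrolment and have ongoing SD cannot count towards CBR, which modestly understates it

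*Protocol*

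**What the plan says.** **When the study may be analysed.** Protocol 4.5 allows analysis and reporting once every patient has met at least one of several conditions. Most describe patients whose course has ended, such as progression, death or withdrawal of consent. The one that fits a patient still on treatment without progression is: "Has been treated until at least 4 weeks after the 1st post-baseline tumor assessment". Patients on treatment at the final cut-off are foreseen, and their later data go into an addendum to the CSR. Protocol 11.4 ties the writing of the CSR to the primary endpoint assessment, which is ORR.

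**When scans are done.** Protocol 8.6 schedules tumour assessments "during the last week of Cycles 2, 4, 6, 8, 10, 12 and every 3 cycles thereafter". Protocol 4.2.2 places a lead-in dose before the combination starts: "Seven days prior to Cycle 1 Day 1 (C1D1) (i.e., at Day -7), patients will receive a single dose of AFM24".

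**What CBR is.** Protocol 8.3.2.5 counts "overall tumor response (CR or PR) or SD for at least 24 weeks". Protocol 9.3.2 says the same and adds that response may be of any duration: "Clinical benefit rate (defined as CR or PR [any duration] OR SD ≥24 weeks".

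**The denominator.** For Phase 2a, SAP 8.6.2 states: "The percentages will be based on the total number of patients in the Full Analysis Set for a given Expansion Arm". The FAS (SAP 7.2) requires some amount of both drugs and sets no minimum follow-up. SAP 8.1 fixes the layout: "Phase 1 summaries will be presented by the dose level, and Phase 2a summaries by Expansion Cohort".

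**The concern.** The 4-week condition suits ORR, because it equals the interval after which Protocol 8.6 asks for a response to be confirmed. It does not suit an endpoint with a 24-week requirement. A patient who starts late, has SD and is still on treatment at an early cut-off cannot yet have 24 weeks of SD. Under the visible definitions that patient stays in the CBR denominator and cannot enter the numerator.

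The resulting error is always downward and depends on when patients enrolled, not on the treatment. It falls mainly on the arm that closes last, so CBRs reported side by side by expansion cohort would rest on unequal follow-up. The addendum does not repair the CBR in the final CSR, and no visible sentence says that CBR will be recalculated there.

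**Working it through.** The documents state no minimum follow-up in weeks, so there is no figure of the plan's own to reproduce. What follows is calendar arithmetic.

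**Inputs from the documents:** 28-day cycles; scans in the last week of Cycles 2, 4, 6 and 8 (Protocol 8.6); 4 weeks after the first scan (Protocol 4.5); Day -7 is 7 days before C1D1 (Protocol 4.2.2); up to 130 patients in four Phase 2a cohorts; 24 to 48 months to enrol and complete Phase 2a (Protocol 4.4).

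**Step 1, scan dates.** The last week of Cycle n runs from (n-1) x 28 + 21 to (n-1) x 28 + 27 days after C1D1.
- Cycle 2: 49-55 days = 7.0-7.9 weeks.
- Cycle 6: 161-167 days = 23.0-23.9 weeks from C1D1, or 24.0-24.9 weeks from Day -7.
- Cycle 8: 217-223 days = 31.0-31.9 weeks from C1D1.

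**Step 2, the floor.** 49 + 28 = 77 and 55 + 28 = 83 days, which is 11.0-11.9 weeks after C1D1 or 12.0-12.9 weeks after Day -7.

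**Step 3, the window of late starters.** The interval from the floor to the qualifying scan is the stretch of late enrolment that is affected.
- Qualifying scan Cycle 6 (SD timed from Day -7): 161 - 77 = 84 days = 12 weeks (11.1-12.9 allowing for the scan day within the week).
- Qualifying scan Cycle 8 (SD timed from C1D1): 217 - 77 = 140 days = 20 weeks (19.1-20.9).

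An arm whose last patient started more than 12-13 weeks (or 20-21 weeks) before the study's last patient loses nothing.

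**Step 4, an illustration of size.** These assumptions are not in the documents: even accrual in four parallel arms of 130/4 = 32.5 patients, 12 weeks from last start to cut-off, and 20% of patients with true SD of at least 24 weeks.
- Accrual period: 24 months = 104.4 weeks, less 12 = 92.4; 48 months = 208.7 weeks, less 12 = 196.7.
- Rate per arm, at 4.35 weeks per month: 32.5/92.4 x 4.35 = 1.5 per month; 32.5/196.7 x 4.35 = 0.7 per month.
- Share of patients short of the scan, 12-week window: 12/196.7 = 6.1% to 12/92.4 = 13.0%. Of 130, that is 7.9 to 16.9 patients.
- Understatement of CBR: 6.1% x 20% = 1.2 points to 13.0% x 20% = 2.6 points.
- Share short, 20-week window: 20/196.7 = 10.2% to 20/92.4 = 21.7%, or 13.2 to 28.2 of 130. Understatement: 2.0 to 4.3 points.

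For scale, the exact (Clopper-Pearson) 95% interval for 6 of 32 is 7.2% to 36.4%.

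**The case against.** **The deciding text may exist.** No visible sentence says that ongoing SD of less than 24 weeks counts as non-benefit. That follows from the definition and the denominator together. SAP Table 1, the text under the missing-data heading and SAP 8.6.1 are not shown, and any of them could hold a rule. This stands and limits confidence. A reader might infer that the plan gives no start date for timing SD, because Protocol 9.3.2 times OS from the first AFM24 dose and PFS from the first dose of both drugs. The documents do not support that inference: Protocol 8.3.2.2 and 8.3.2.3 time both from the initial date of treatment, and the SD rule may lie in the unseen text.

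**Protocol 4.5 is a floor.** Nothing shows that the sponsor would cut off at it, and the addendum and Protocol 11.4 are further safeguards. This stands in part. A later cut-off shrinks the bias, but neither safeguard requires 24 weeks of follow-up for CBR in the final CSR.

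**The Cycle 8 case is fragile.** The last Cycle 6 scan day is 167 elapsed days after C1D1, one short of 168. If both end dates are counted, it is day 168 and can qualify. The 20-week figures are therefore an alternative, not the main result.

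**The illustration could be pushed higher.** A reader might infer a much larger effect in a fast-recruiting last arm. The documents give no accrual rate by arm, and the duration in Protocol 4.4 implies only about 0.7-1.5 patients per arm per month under even, parallel accrual.

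**Other outputs show durability.** Swimmer plots and Kaplan-Meier PFS do so, which stands. A reader might add that CBR is the only tabulated response rate with a minimum SD duration, but SAP Table 1 could set a minimum for SD generally.

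**Conclusion.** The point holds conditionally and is minor. If the final cut-off is at or near the Protocol 4.5 floor, and no unseen rule intervenes, CBR is understated because patients from about the last 12 weeks of enrolment with ongoing SD cannot qualify. The effect falls mainly on the arm that finishes enrolling last. Its size is about 1.2-2.6 percentage points, or about 2.0-4.3 if Cycle 8 is the qualifying scan. Both ranges rest on the assumed arm size, accrual and SD share, and on scans done on schedule. The bias is small against the sampling error of an arm of this size, but it is systematic and avoidable.

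It would be too strong to conclude that the reported CBR will be wrong, or that a trial decision is at risk. The cut-off may come later. Where formal testing is planned ("A Simon two-stage optimal design will be utilized for EXP-1 and EXP-2"), the primary endpoint is ORR; CBR is secondary and no visible decision rule uses it.

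**What to change.** In SAP 8.6.2, keep the all-FAS CBR and add one row per arm: CBR among FAS patients whose treatment start was early enough before the cut-off to reach the first scheduled scan at or after 24 weeks, on whatever SD clock the SAP uses. From the scan dates above, that means Day -7 at least 25 weeks before cut-off if Cycle 6 is the qualifying scan, or C1D1 at least 32 weeks before cut-off if it is Cycle 8. Select by start date only, whatever the outcome, and show the number excluded. Removing only patients with ongoing SD would bias the rate the other way. If SAP Table 1 or the missing-data section already contains an equivalent rule, a reference to it is enough.

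The cost is one extra row per arm and a smaller denominator. Pooled, at the earliest cut-off, about 8-17 fewer of 130 patients contribute if Cycle 6 qualifies, or about 13-28 fewer if Cycle 8 does, mostly in the last arm to finish. The cut-off date does not move.
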